9.3 Patient Evaluability

9.3.1 Definition of a patient evaluable for the primary endpoint

A patient will be considered evaluable for the treatment success endpoint (section 9.1.1) if (s)he receives any portion of treatment, except if treatment or follow-up is terminated for reasons unequivocally unrelated to treatment toxicity (e.g., if a drug is omitted from the regimen for reasons aside from toxicity, or treatment is terminated because of problems unequivocally related to disease progression). Patient who are not evaluable for the primary endpoint will be replaced.

9.3.2 Definition of a patient evaluable for toxicity:

Any patient who receives at least one dose of any drug on study will be considered evaluable for toxicity.

9.3.3 Definition of a patient evaluable for response:

A patient will be considered evaluable for response if the patient receives all or part of protocol therapy and the patient is under follow-up for a sufficient period to evaluate the disease at the end of protocol therapy or to meet the definition of progressive disease. A patient who dies as a result of toxicity after receiving all or part of protocol therapy, or who is removed from therapy for problems possibly related to disease progression, will be considered a non-responder.

9.4 Definition of toxic death (TD)

Any death that is not clearly related to disease progression that occurs during protocol therapy or during recovery following protocol therapy, or prior to commencing subsequent non-protocol course of therapy, will be considered a toxic death for the purposes of this study.

9.4 Statistical Analysis

9.4.1 Treatment success rate: Given the small sample size in each cohort, the treatment success rate will only be estimable imprecisely within each cohort and overall.

9.4.2 Toxicity: The analysis of toxicity will be primarily descriptive, comprising tabulation of the fraction of patients who experience grade 3 or grade 4 toxicities.

9.4.3 Efficacy: Given the small sample size in each cohort, the CR/CRi rates and the MRD-negative rates will only be estimable imprecisely within each cohort and overall.

9.4.4 Pharmacokinetics analysis: The precision with which a detailed pharmacokinetic analysis of vincristine levels after exposure to Marqibo® in the context of UK ALL R3 treatment or maintenance therapy in this population of patients can be performed will depend on the number of patients who participate in the optional Day 1 PK component of this study, which includes sampling at end of infusion, 3 hours and 24 hours in addition to the mandatory day 8 and day 15 samples (applicable to only the UK ALL R3 with or without mitoxantrone arms A & B). Patients enrolled to arm C will only have pre-dose #1 (30 minutes before start of infusion (SOI) and a trough level at day 8 during the first cycle. Assuming first order elimination, these pharmacokinetic analyses will include estimation of total vincristine concentration, area under the curve through 168 hours, and, the half-life of vincristine when Marqibo® is given with combination therapy. However, the two mandatory samples at day 8 and 15 taken prior to the second and third dose of Marqibo®, representing vincristine trough levels, will be obtained on all patients. There are no data currently available to estimate interpatient variability of vincristine levels from Marqibo® in children, but data from²³ in adults indicate that the coefficient of variation (CV) of vincristine at trough levels will be approximately 100%. Hence, assuming that the study proceeds to the second stage, and that 25/30 patients are evaluable for PK assessment, the precision of the estimate of mean trough levels of vincristine at each of these times point will be CV=17%, resulting in a 95% confidence interval with bounds within 40% of the population value. This provides sufficient precision for meaningful comparison of vincristine concentration in this study to published adult study as well as the ongoing Marqibo® Phase I study in children. These analyses will be based on the total vincristine exposure and will not include distinguishing between the free and liposomal bound components.

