1.2 Exploratory Objectives

- 1.2.1 To describe the constellation of toxicities experienced by patients treatment with each of these three regimens.
- 1.2.2 To describe the number of patients who achieve a complete remission (CR), including CR + CR with incomplete blood count recovery (CRi) rate for patients with acute lymphoblastic leukemia (ALL) and first to third relapse who are treated in cohorts A and B.
- 1.2.3 To describe the number of patients with CR at end of induction who become minimal residual disease (MRD) negative by flow cytometry (i.e., $< 10^{-4}$ blasts in a central lab) in cohorts A and B.
- 1.2.4 To assess the pharmacokinetics of Marqibo® when used in combination with the UK ALL R3 induction chemotherapy regimen, in UK ALL R3 induction chemotherapy without mitoxantrone, and in ALL maintenance therapy.

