Clinical studies and FDA approval: Marqibo® has been evaluated in more than a dozen clinical trials in over 600 subjects (primarily adults) with ALL, non-Hodgkin lymphoma, and other cancers. Clinical experience indicates that Marqibo® can be administered safely at individual and cumulative doses exceeding those typically employed for standard vincristine and may provide anticancer activity without increased toxicities. It has been used both as a single agent as well as in conjunction with combination chemotherapy. Phase I studies established safe dosing for monotherapy.⁵ In 2012 the US Food and Drug Administration (FDA) granted accelerated approval of Marqibo® for adults with relapsed and refractory Philadelphia chromosome-negative ALL.⁶ This approval was based on a pivotal Phase II study (rALLY trial) in which Marqibo® was administered as a single agent weekly at a dose of 2.25 mg/m² without a dose cap. There was a 20% (13/65) CR/CRi rate and an overall response rate (ORR) of 35% (23/65; 13 CR/CRi, 4 morphologic remissions without blood count recovery, and 6 partial responses).⁷ Eight of the 13 patients achieving CR/CRi achieved MRD negative status. Responses were seen in both T- and B-lineage ALL.

Pediatric studies: A small Phase II study was conducted in children (P99-401). Marqibo® was well tolerated and some activity was seen, although data were quite limited. Subjects were treated with Marqibo at 2.0 mg/m² IV over 1 hour every 14 days ± 2 days (1 cycle). Only 1 subgroup (sarcomas) fully accrued prior to termination of this study. Only one patient with ALL was treated on that trial. Of the 29 dosed and evaluable subjects, the responses to treatment were as follows: 2 subjects had a PR (7%), 8 subjects had stable disease (28%) and 19 subjects had disease progression (66%). Seven (24%) subjects were alive at the last protocol specified survival follow-up. The median time to progression was 52 days for all subjects. Only 1 subject experienced a possibly related Grade 3 or higher neurologic event (peripheral neuropathy). Results of this study were never published beyond abstract form.⁸

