There are currently two ongoing Phase III trials in adults patients with newly diagnosed ALL and NHL utilizing combination chemotherapy with Marqibo®. Preliminary results from these trials

support safety with the use of Marqibo® with combination therapy. (Clinicaltrials.gov: NCT01439347 and NCT01478542)

Toxicity: In its standard formulation, vincristine neurotoxicity is dose-dependent and symmetrical, and is manifested as both peripheral sensory and motor neuropathy. Progressive neuropathy may occur, leading for example to weakness with foot and wrist drop. Vincristine induced peripheral neuropathies are generally reversible although recovery may take months and is often incomplete.

The major side effects of Marqibo® are due to the active vincristine component, Thus, the most common treatment-related adverse events of Marqibo® have been neurological. Adverse events occurring in greater than or equal to 30% of patients treated with single agent Marqibo® include neuropathy, constipation, nausea, neutropenic fever, pyrexia, decreased appetite, and diarrhea.

Patients with ALL who receive Marqibo® will generally have received vincristine previously and cumulative toxicity from prior vincristine exposure is possible. On the single-agent Phase II rALLY trial, all patients had prior vincristine exposure and patients received a median of four doses of Marqibo® at nearly twice the usual dose intensity of standard vincristine. Some received up to 70 mg total vincristine exposure. Notably, 77% had prior neuropathy at study entry. Despite that, the observed neurotoxicity was comparable to that seen with standard vincristine. 86% had some neuropathy, but Grade 3 neurotoxicity was observed in only 23% of patients. Thus, even in patients with prior vincristine exposure, Marqibo® was fairly well tolerated. Other significant adverse events observed on the rALLY trial were neutropenic fever and tumor lysis syndrome.⁷ Such patients may also have experienced prior hepatotoxicity, which in the setting of Marqibo® administration, risk for hepatotoxicity may be increased in combination with other hepatotoxic chemotherapeutic agents and thus all subjects will be monitored daily.

There is the potential of toxicity to liposome carrier (sphingomyelin/cholesterol) as these are biological lipids that are important components of plasma membranes. However, no toxicity has been observed in pre-clinical toxicology studies conducted with empty liposomes in mice, rats and dogs.

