9.1.2 Exploratory Endpoints

- a. Occurrence of toxicity, as graded using the NCI's Common Terminology Criteria for Adverse Events (CTCAE 4.03).
- b. (Cohorts A and B) Achievement of CR or CRi during the course of therapy.
- c. (Cohorts A and B) In those who achieve CR or CRi, achievement of MRD negative status (i.e., $<10^{-4}$ blasts by flow cytometry in a central lab).
- d. Pharmacokinetic assessment of Marqibo®

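### The toxicity objective and endpoint have no grade limit and grades 1–5 are collected, but the planned table in 9.4.2 covers grade 3 or 4 only, so lower-grade neuropathy falls outside the planned analysis

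*Combined protocol and SAP*

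**What the plan says.** **Objective and endpoint.** Section 1.2.1 sets the aim: "To describe the constellation of toxicities experienced by patients treatment with each of these three regimens". Section 9.1.2(a) defines the matching endpoint as "Occurrence of toxicity, as graded using" CTCAE 4.03. Neither has a grade floor.

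**Data.** Section 12.1 asks sites to enter toxicities of grades 1 to 5 in the eCRF, including changes of grade. Section 7.1 requires a neurological examination and its form before enrollment, before treatment, weekly on treatment and at the final visit.

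**Analysis.** Section 9.4.2 calls the toxicity analysis primarily descriptive, "comprising tabulation of the fraction of patients who experience grade 3 or grade 4 toxicities". No other section plans a summary of grade 1–2 events or a separate neuropathy analysis.

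**A third wording.** Section 9.0 lists, as a secondary objective, estimating the rates of serious toxicities. Section 1.2 has no secondary objectives, only exploratory ones.

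**Why neuropathy matters here.** Section 2.4 hypothesizes that the combination may show better safety than historical regimens and specifies neurotoxicity. Section 6.1.3 names neurotoxicity as the dose-limiting toxicity of Marqibo and describes it as starting with sensory symptoms.

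**The concern.** An endpoint without a grade limit is paired with an analysis that has one. If 9.4.2 is followed as written, grade 1–2 events are collected but enter no planned table. For most drugs that would be a minor loss of detail. For a vincristine formulation the characteristic toxicity has a substantial low-grade component, and grade 2 is not trivial: Appendix 5 defines grade 2 motor and sensory neuropathy as moderate symptoms that restrict instrumental activities of daily living.

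The rest of the plan does not fill the gap. With 6 to 12 evaluable patients per cohort and dose level, a severe-grade table may show few or no neuropathy events while several patients have lower-grade neuropathy. If lower-grade summaries are chosen only after the data are seen, a reader cannot tell whether the choice was selective.

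**Working it through.** The plan states no figure to reproduce; the check compares texts and adds simple proportions.

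**1. Where would grade 2 neuropathy appear?**

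| Section | Grades covered |
|---|---|
| 1.2.1, 9.1.2(a) objective and endpoint | any |
| 12.1 data entry | 1–5 |
| 9.0 wording of objective | serious toxicities |
| 9.4.2 planned table | 3 or 4 |
| 4.2.1.1 non-hematological DLT | 3 or greater |
| 4.3.1.1 Marqibo changes for neuropathy | none below grade 3 |
| 11.3.1 expedited reporting | 5; related 4; unexpected related 3 |

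Grade 2 neuropathy is in the objective, the endpoint and the database, but in none of the lower five rows unless it is serious in the sense of 9.0. It could reach the primary endpoint only indirectly, if a patient fell short of the minimum doses in 9.1.1. That is unlikely for Marqibo, because neuropathy below grade 3 changes no dose.

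**2. Illustration of the share below grade 3.** Section 2.2 says of the adult single-agent Phase II trial: "86% had some neuropathy, but Grade 3 neurotoxicity was observed in only 23% of patients".

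- Share of affected patients below grade 3 = (any grade − grade 3) / any grade = (86 − 23) / 86 = 63/86 = 73%. This treats 23% as the grade 3–4 rate, because no grade 4 rate is given.
- Allowing for rounding: (85.5 − 23.5)/85.5 = 72.5% to (86.5 − 22.5)/86.5 = 74.0%.
- Consistency check: the response rate in section 2.2 uses 65 patients ("There was a 20% (13/65) CR/CRi rate"). Assuming the same denominator, 56/65 = 86.2% and 15/65 = 23.1% match the stated percentages, and (56 − 15)/56 = 41/56 = 73.2%.
- Sensitivity: with grade 3 at 23%, most affected patients are below grade 3 whenever any-grade neuropathy exceeds 2 × 23% = 46%.

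**3. What those rates would look like at this trial's sizes.**

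| Evaluable patients | Any grade (×0.86) | Grade 3 (×0.23) | Outside the table (×0.63) | P(no grade 3) |
|---|---|---|---|---|
| 6 | 5.2 | 1.4 | 3.8 | 0.77^6 = 21% |
| 12 | 10.3 | 2.8 | 7.6 | 0.77^12 = 4% |

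The earlier pediatric Phase II study reports one possibly related neurologic event of grade 3 or higher. If its 29 dosed and evaluable subjects are the denominator, that is 1/29 = 3.4%, and 12 patients would show none with probability (28/29)^12 = 66%.

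**4. Limits of the illustration.** Of the adult trial, section 2.2 adds: "Notably, 77% had prior neuropathy at study entry". On a common denominator, patients with neuropathy on study but none at entry made up at least 86 − 77 = 9 and at most 100 − 77 = 23 percentage points. Much of the 86% was therefore present at entry, and the 63 points mix grade 1, grade 2 and pre-existing neuropathy.

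**The case against.** **Section 9.4.2 fits section 9.0.** A severe-grade table broadly answers an objective about serious toxicities. That is fair, but it moves the inconsistency rather than removing it: 9.0 then conflicts with 1.2.1 and 9.1.2(a), so all the wordings need aligning.

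**Descriptive leaves latitude.** An analyst could add lower grades. True, but the sentence goes on to define the content as grade 3 or 4, and nothing commits anyone to more.

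**A severe-grade table suits the comparators.** The toxicity figures in section 2.3 for UK ALL R3 and COG reinduction are mostly for grade 3 or higher, and section 9 plans no formal historical comparison. This stands. The severe-grade rows should stay; the case is for adding the lower grades.

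**A reader might infer that low-grade neuropathy would go unreported.** The documents do not support that. Grades 1–5 are entered in the eCRF, non-serious events go to safety meetings (12.2), toxicities go into the DSMC progress report (12.3), and neuropathy below grade 3 is to be closely monitored (4.3.1.1). The gap is in the planned analysis, not in capture or oversight.

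**A reader might also take limiting neuropathy as what the trial tests.** The primary objectives are safety and feasibility; less neurotoxicity is something section 2.4 says the data may show.

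**A reader might take 73% as the expected share of new grade 2 neuropathy here.** No grade 2 rate is given. The source is adult and single-agent, with a median of four doses at 2.25 mg/m². This trial excludes persistent neuropathy of grade 2 or higher at entry (3.4.8), uses combination therapy, and gives one Marqibo dose per cycle in Cohort C.

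**Conclusion.** The mismatch is real and follows from the text alone: objective, endpoint and data collection span all grades, while the planned table covers two. Grade 1–2 toxicity, including grade 2 neuropathy, lies outside the planned analysis, the DLT definition and the Marqibo dose rules.

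Its size in this trial cannot be estimated from the documents. The 73% shows only that a severe-grade cut can exclude most patients with neuropathy. It rests on a common denominator for the adult percentages and on grade 3 standing for grade 3–4.

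The point concerns an exploratory endpoint. It does not affect the primary endpoint, sample size or monitoring rules. It should still be corrected, because neurotoxicity is the safety question named in section 2.4 and the change is cheap.

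**What to change.** - **9.4.2:** tabulate the maximum CTCAE grade per patient, grades 1–5, for all toxicities, by cohort and dose level. This also brings in grade 5, which the present sentence omits.
- **Neuropathy:** show peripheral sensory and peripheral motor neuropathy separately, each as any grade, grade 2 or higher, and grade 3 or higher.
- **Baseline:** show change from baseline for neuropathy, using the pre-treatment neurological examination and the eligibility assessment under 3.4.8.
- **9.0:** align the wording on serious toxicities, and the label of secondary objective, with 1.2.1 and 9.1.2(a).

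**Cost.** The table is longer; the on-treatment grades are already collected. The baseline column needs some work. The Appendix 4 form records normal or abnormal with a description and has no grade field, and adverse event collection starts with the first dose (11.2). A pre-treatment neuropathy grade must therefore be recorded, or derived from the examination form using Appendix 5. For patients already enrolled this may mean going back to existing records. No treatment rule changes.

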Outcomes for patients treated with the UK ALL R3 induction regimen reported to date have been for patients in first relapse on ALL. On this protocol, patients with first to third relapse will be eligible and thus many are likely to be more heavily treated and at greater risk of toxicity than previously reported patients. Limited data reporting on the experience with the UK ALL R3 induction regimen in multiply relapsed patients who had received at least two prior treatment attempts demonstrated that there was no appreciable difference in the grade ≥ 3 toxicities between first and multiply relapsed patients. However, amongst this group of patients, grade ≥ 3 infection was reported in 53/59 (90%) patients and 55/59 (97%) of patients experienced at least one grade ≥ 3 non-hematologic adverse event.¹² Importantly, in this recent retrospective review, 7% (3/42) of patients treated with the UK ALL R3 induction regimen in first relapse had a delay in starting their next treatment course beyond day 49 (95% CI 1.5% - 19.5%), and 38% (6/16) of patients treated in second or greater relapse were similarly delayed (95% CI 15% - 65%).

Toxicity data were reported on a completed COG trial of 4-drug reinduction chemotherapy (COG AALL 01P2) in patients with first or greater relapse.^{13, 14} This frequency of nonhematologic Grade 3 and 4 toxicities ranged up to 58%. The post-induction toxic death (TD) rate prior to modification of the regimen was 14% ($n=3$).¹³ On a Phase II trial of single agent clofarabine in children with ALL who were in a second relapse or beyond, inclusive of those with post-transplant relapse, 8% ($n=5$) of subjects experienced a TD that was considered at least possibly related to study drug.¹⁵ Similarly on a Phase II study that incorporated bortezomib with combination chemotherapy in patients who were in second relapse or beyond, including those with post-transplant relapse there was a 14% ($n=3$) TD rate, primarily due to infection associated complications.¹⁶ Based on these data, we anticipate at least a 10% toxicity death rate on this trial. We also would consider it unacceptable should 45% of subjects not be able to proceed to further therapy by day 49 due to toxicity of any grade.

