4.2 Dose Limiting Toxicity

Toxicity will be graded using the CTCAE criteria, version 4.03. The CTCAE provides descriptive terminology and a grading scale for each adverse event listed. A copy of the CTCAE can be downloaded from the CTEP home page (<http://ctep.cancer.gov>). Any dose-limiting toxicity (DLT) should be reported immediately through the TACL Operations Center to the Study Chair or Vice Chair. In addition to CTCAE, grading of sensory and motor neuropathies will be augmented by definitions listed in Appendix 5.

4.2.1 Definition of DLT: Dose limiting toxicity (DLT) will be defined as the occurrence of non-hematologic DLT and/or hematologic DLT as defined below.

4.2.1.1 Non-hematological DLT:

(Cohorts A and B) Any Grade 3 or greater non-hematological toxicity that is possibly, probably or definitely attributable to the protocol regimen and prevents a patient from receiving the required number of doses of therapy (as specified in Section 9.0) or from proceeding with further therapy by day 49 of the treatment cycle.

(Cohort C) Any Grade 3 or greater non-hematological toxicity that is possibly, probably or definitely attributable to the protocol regimen and prevents a patient from receiving the required number of doses of therapy (as specified in Section 9.0) or from proceeding with further therapy by day 21 of the treatment cycle for Stratum C.

4.2.1.2 Hematological DLT:

(Cohorts A and B) The absence of peripheral blood count recovery (ANC >500/ μ L and platelet count > 20,000/ μ L) 7 weeks (49 days) after the start of chemotherapy in the absence of persistent leukemia or documented myelosuppressive infection. Subjects with abnormal blood counts (Grade 1 through 4) at baseline due to disease will not be evaluable for hematologic DLT and will be considered not having had hematologic DLT for the purposes of the definition in 4.2.1.

(Cohort C) The absence of peripheral blood count recovery (ANC > 500/ μ L and platelet count > 20,000/ μ L) 3 weeks (21 days) after the start of chemotherapy in the absence of persistent leukemia or documented myelosuppressive infection. Subjects with abnormal blood counts (Grade 1 through 4) at baseline due to disease will not be evaluable for hematologic DLT and will be considered not having had hematologic DLT for the purposes of the definition in 4.2.1.

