9.1.3 Safety Endpoints

Toxic Death (TD): Any death that is not clearly related to disease progression or to external causes (e.g. accident) that occurs during protocol therapy or during recovery following protocol therapy, or prior to commencing subsequent non-protocol course of therapy, will be considered a toxic death for the purposes of this study.

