9.5 Interim Monitoring of Toxic Death

The occurrence of toxic death (TD) per 9.3.4 will be a primary endpoint for safety monitoring. Based on prior studies, a 10% TRM rate in patients with advanced ALL is expected (see section 2.3). Hence a population toxic death rate that exceeds 10% will be considered unacceptable. No formal statistical monitoring will be employed. Rather, an observed TD rate that exceeds 10% at any time in any cohort will result in immediate suspension of the study, at which time the cause and circumstances of the death and its attribution to the study regimen will be reviewed with the study committee and with the Data and Safety Monitoring Committee (DSMC) to determine

whether modifications to or termination of the study is warranted. Operationally, this criterion will be satisfied if within a cohort, a TD is observed, and the nominal rate exceeds 10%.

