12.0 DATA AND SAFETY MONITORING

12.1 Data Submission

All study data will be submitted via electronic data capture forms using the DataLabs/TACL Website. All toxicities grades 1-5, heme and non-heme with grade fluctuations should be reported in the eCRF. Please refer to the TACL web site <https://tacl.chla.usc.edu> for T2012-002 CRF Completion Guide or contact the TACL Operations Center at [contact] if you need assistance.

The following are required to be submitted to the Operations Center for all patients entered:

Copies of following: Roadmaps and Bone Marrow Reports (include both aspirate and biopsy reports). These de-identified forms are to be emailed to the TACL Operations Office at [contact] at the end of the study course.

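### Section 9.4.2 limits the toxicity table to grades 3 and 4 and gives no per-patient counting rule, so fatal (grade 5) events can be missing from the event-type fractions

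*Combined protocol and SAP*

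**What the plan says.** The only planned analysis of toxicity by grade is in section 9.4.2: "tabulation of the fraction of patients who experience grade 3 or grade 4 toxicities". It gives no rule for a patient with several grades of the same event. Section 9.4 plans no final summary of grade 5 events or toxic deaths.

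Other sections use a wider range of grades:

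- The exploratory endpoint in 9.1.2 has no upper limit: "Occurrence of toxicity, as graded using the NCI's Common Terminology Criteria for Adverse Events (CTCAE 4.03".
- The non-hematological dose-limiting toxicity (DLT) definition in 4.2.1.1 is open at the top: "Any Grade 3 or greater non-hematological toxicity that is possibly, probably or definitely attributable to the protocol regimen".
- Section 12.1 collects the full range: "All toxicities grades 1-5, heme and non-heme with grade fluctuations should be reported in the eCRF".

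Fatal toxicity is expected and has its own provisions. Section 2.3 says "we anticipate at least a 10% toxicity death rate on this trial", and section 9.5 says "a 10% TRM rate in patients with advanced ALL is expected". Section 9.1.3 defines which deaths count ("will be considered a toxic death for the purposes of this study"), and 9.5 monitors them: "The occurrence of toxic death (TD) per 9.3.4 will be a primary endpoint for safety monitoring". Under 9.3.2, anyone given at least one dose of any study drug is evaluable for toxicity.

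**The concern.** A table cut off at grade 4 can leave out the most severe form of the event it describes. A patient who dies of infection may be absent from the severe-infection fraction yet present in its denominator, so any error is downward. The toxic-death count does not repair this. It gives a number of deaths, but it does not return each one to the fraction for infection, hepatic toxicity or whichever event was fatal.

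The missing counting rule adds to the problem. Worst grade and any occurrence are both reasonable conventions, but they give different fractions when an event passes through grade 3 or 4 before becoming fatal. Two analysts following 9.4.2 could report different rates from the same data.

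The cut-off also leaves out grade 2 neuropathy. Section 2.4 names neurotoxicity as the respect in which safety may improve on historical regimens. Objective 1.2.1 is to describe the range of toxicities seen with each regimen.

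**Working it through.** The plan gives no figure that depends on this table, so there is none to reproduce. The check has three parts: which patients can be omitted, how much each omission matters, and how likely the situation is.

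**1. Who can be omitted**

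| Patient's record for one event type | Any-occurrence counting | Worst-grade counting |
|---|---|---|
| Grade 3 or 4, not fatal | counted | counted |
| Grade 3 or 4 recorded, later grade 5 | counted | omitted |
| Recorded only at grade 5 | omitted | omitted |

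In each row the patient stays in the denominator (9.3.2).

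**2. Size of one omission**

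Section 9.0 plans 6 evaluable patients per cohort and dose level, with a maximum of 12. One patient is worth 1/n:

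- n = 6: 1/6 = 16.7 points
- n = 12: 1/12 = 8.3 points

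As an illustration with assumed counts, suppose 4 of 12 patients have a worst grade of 3 or 4 for some event and 1 more has grade 5. The grade 3–4 fraction is 4/12 = 33.3%. The grade 3–5 fraction is 5/12 = 41.7%.

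**3. Chance of at least one toxic death**

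The expected number is n × p, and the chance of at least one is 1 − (1 − p)^n. Sections 2.3 and 9.5 give p = 10%. The range comes from rates cited in section 2.3: 4% (8 induction deaths among 201 patients on the mitoxantrone backbone) to 14% (the COG reinduction trial and the bortezomib trial).

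| p | n = 6: expected | n = 6: at least one | n = 12: expected | n = 12: at least one |
|---|---|---|---|---|
| 4% | 0.24 | 21.7% | 0.48 | 38.7% |
| 10% | 0.60 | 46.9% | 1.20 | 71.8% |
| 14% | 0.84 | 59.5% | 1.68 | 83.6% |

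At 10%, for example, 1 − 0.9^6 = 0.469 and 1 − 0.9^12 = 0.718. These are chances of a toxic death. They bound the chance that such a death produces an omission, because under any-occurrence counting some fatal cases are still counted.

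**4. Neuropathy**

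In the adult single-agent trial described in section 2.2, 86% had some neuropathy and 23% had grade 3. The difference, 86 − 23 = 63 points, would not appear in a grade 3–4 table. The documents do not split it between grades 1 and 2, and 77% already had neuropathy at entry, so a grade 2 threshold would recover an unknown part. Here, section 3.4.8 excludes persistent neuropathy of grade 2 or more at entry, so grade 2 on study would generally be new or worse.

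**The case against.** The strongest reply is that fatal toxicity is well covered elsewhere. Toxic death is a separate safety endpoint (9.1.3). An observed rate above 10% in any cohort suspends the study, with review of the cause (9.5). Grade 5 events need expedited reporting whatever their cause (11.3.1), and deaths on study go to the DSMC (12.3). All of this stands. It does not fill the gap in the planned table, since these provisions concern oversight and 9.4 schedules no final summary of them.

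A second reply is that the wording of 9.4.2 contains no worst-grade rule, and 12.1 asks for grade fluctuations. Read literally, a patient who had grade 3 or 4 sepsis and then died of it is still counted. This also stands. A reader might infer that every fatal case necessarily drops out, but the documents do not support that. It happens only under worst-grade counting, or when no grade 3 or 4 stage was recorded.

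A reader might also infer that the primary safety result is biased. It is not. The primary endpoint is treatment success (9.1.1), which fails on a DLT, and the non-hematological DLT definition has no upper grade. Section 9.4.2 serves an exploratory endpoint.

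Nor does the plan schedule a formal comparison of these fractions with section 2.3. The historical figures there use mixed conventions. The extended mitoxantrone-arm data count grades 3 to 5 (135 of 201, 67%), while the COG reinduction trial gives grades 3 and 4 with toxic deaths separate. Showing grades 3, 4 and 5 separately serves both.

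Finally, the 10% rate comes from reinduction and advanced-disease trials, whereas section 9.2 expected Cohorts B and C to be less toxic than Cohort A. The lower row of the range may suit those cohorts better.

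**Conclusion.** The point holds as a minor one. Section 9.4.2 sets a cut-off narrower than the grades collected and narrower than the DLT definition, and it leaves the counting rule open. The result can be a downward error of 8.3 points (n = 12) or 16.7 points (n = 6) per omitted patient in the fraction for the event type concerned. At the protocol's 10% rate, a cohort has about a 72% (n = 12) or 47% (n = 6) chance of at least one toxic death.

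These figures assume independent patients, a common death rate, and a toxicity denominator equal to the planned evaluable numbers. Because patients not evaluable for the primary endpoint are replaced (9.3.1), the toxicity denominator may be somewhat larger and the shift per patient slightly smaller.

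The documents do not support saying that deaths go unreported, that the regimen will be declared safer than it is, or that any decision rule is affected. The neuropathy addition is a matter of matching the table to the hypothesis in 2.4; nothing in the plan commits it to a grade 2 threshold.

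**What to change.** Reword 9.4.2 along these lines:

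- Among toxicity-evaluable patients (9.3.2), tabulate the maximum CTCAE grade per patient and event type, by cohort and dose level.
- Report the fraction with grade 3 or higher, with grades 3, 4 and 5 shown separately.
- Report the number and fraction of toxic deaths by cohort and dose level, with the event judged fatal. Cite the definition in 9.1.3; section 9.5 currently points to a section 9.3.4 that does not appear.
- For sensory and motor neuropathy, also report grade 2 or higher, graded by Appendix 5. Appendix 4 records examination findings, not grades.

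The cost is a few sentences. Grades 1 to 5 are already collected and neurological examinations are already weekly, so no new data are needed. Sample size, endpoints and monitoring rules stay as they are.
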